#### 4. TREATMENT PLAN

Potential subjects who preliminarily meet inclusion criteria and exclusion criteria as determined by study staff (for example, the investigator or clinical research coordinator) will meet with study staff to review the study and informed consent in detail. At this time, inclusion and exclusion criteria will be confirmed with the subjects and treating clinicians as necessary.

All eligible subjects (meeting criteria described in Section 3) will receive the drug combination of infigratinib with tamoxifen. Once a dose level for infigratinib is determined, Cohort 1 will close.

All subjects in whom a research biopsy of a disease site is deemed feasible and safe by the investigator will be required to undergo a biopsy to donate 4 to 8 cores of tumor tissue before and on-treatment to be used for research purposes, including genomic/transcriptomic/proteomic analysis and organoid culture derivation as described in Section 2.6. The on-treatment biopsy is recommended to occur on Day 15 of treatment, but any time on treatment is acceptable. Tissue will be transported to the [name] lab for processing and analysis. Subjects who require a tumor biopsy for eligibility assessment will undergo the collection of tissue cores for research simultaneously, whenever possible. Archival tumor tissue, including stored at Stanford University and at other institutions, may be obtained for use for tissue correlative studies as well. Only tissue not needed for diagnostic purposes will be used for research.

Subjects in Cohort 1 will receive tamoxifen 20 mg orally continuously starting on Day 1 and will additionally receive infigratinib orally daily 3 weeks on, 1 week off (28-day cycle) at the dose level dictated by study protocol (125 mg, 100 mg, or 75 mg).

Subjects will continue receiving cycles as above until 18 months on treatment, progression, or unacceptable toxicity (or other reasons outlined in Section 4.3). If toxicity is deemed per the investigator to be related to endocrine therapy (tamoxifen) and not infigratinib, subjects will be given the option of continuing infigratinib only (without endocrine therapy) until progression.

Details on study procedures during Screening, Treatment, and Post-Treatment are provided in the Study Calendar and footnotes (Section 9).

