# 7.3 Adverse Events Reporting

Adverse events (AEs) will be documented and recorded at each scheduled or unscheduled visit, including end-of-treatment and during follow-up, using NCI CTCAE v5.0. Subjects will be followed for AEs for 30 days after the last treatment administration or until all drug-related toxicities have resolved (or the Investigator determines in his/her clinical judgment that no further improvement is expected), whichever is later. For serious adverse events (SAEs), the active reporting period will be from the time that the subject provides informed consent, which is obtained prior to the subject's participation in the study, ie, prior to undergoing any study-related procedure and/or receiving investigational product, through and including 30 calendar days after the last administration of the investigational product. SAEs experienced by a subject after the active reporting period has ended should be reported if the Investigator becomes aware of them.

Conditions already present at the time of informed consent should be recorded in the Medical History CRF.

AEs (including lab abnormalities that constitute AEs) should be described using a diagnosis whenever possible, rather than individual underlying signs and symptoms. When a clear diagnosis cannot be identified, each sign or symptom should be reported as a separate AE.

The following information is to be captured in the CRF for each AE: severity grade (CTCAE v5.0, Grade 1 to 5); duration (start and end dates); relationship to study drug (infigratinib or tamoxifen) (reasonable possibility that AE is related: No, Yes); action taken with respect to study drug (none, dose reduction, temporarily interrupted, permanently discontinued, unknown, not applicable); whether medication or therapy was given (no concomitant medication/non-drug therapy given, concomitant medication/non-drug therapy given); outcome (not recovered/not resolved, recovered/resolved, recovering/resolving, recovered/resolved with sequelae, fatal, unknown); and whether the event is serious and seriousness criteria.

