#### 10. MEASUREMENTS

### 10.1 Primary endpoint:

The primary endpoint is the incidence of dose-limiting toxicities (DLTs) in the first 2 cycles of therapy at a specific dose. In Cohort 1, in a subset of subjects who start at infigratinib 100 mg and complete 2 cycles with no DLTs and who remain on study for Cycles 3 and 4, the dose of infigratinib will be increased to 125 mg starting with Cycle 3 and the number of DLTs in Cycles 3 and 4 will be counted toward the primary endpoint (for the 125 mg dose), in addition to the number of DLTs in Cycles 1 and 2 (for the 100 mg dose). For all other subjects, the primary endpoint will be the number of DLTs in Cycles 1 and 2.

DLTs will be graded using NCI CTCAE (Common Terminology Criteria for Adverse Events), v5.0. DLTs will be defined as an adverse event (AE) or abnormal laboratory value at least possibly related to therapy with infigratinib including those AEs and abnormal laboratory values that result in a failure to meet the criteria for re-treatment. The criteria for defining a DLT, which are pre-specified based on the pre-clinical toxicity of infigratinib, are listed in Table 7.

Individual subjects who had a DLT may be retreated, after recovery, at the next lowest dose level.

Investigators will notify QED Therapeutics within 7 days of any DLTs observed.

**Table 7.** Criteria for defining dose-limiting toxicities

TOXICITY	DLT CRITERION
Skipped/ delayed dose	The inability to administer infigratinib on ≥ 75% of scheduled treatment days during cycle 1 at that dose (ie, ≥ 16 days of the 21 days of planned treatment) due to unresolved adverse event of any grade and considered at least possibly, probably, or definitely related to the study drug.
	Delay in 2 nd cycle administration at that dose due to failure of recovery from a possibly, probably, or definitely related adverse event to Grade ≤ 1 or baseline by Day 43 (Day 28 of Cycle 1 + 15 days), except for alopecia.
Blood/ bone marrow	Neutropenia     • Febrile, CTCAE Grade ≥ 3.     • CTCAE Grade ≥ 3 for > 7 consecutive days
	Thrombocytopenia
	Anemia CTCAE Grade 4
Renal/ genitourinary	Creatinine:  • CTCAE Grade 1 for > 7 consecutive days and serum inorganic phosphorus  > 5.5 mg/dL and/or serum total calcium x serum inorganic phosphorus  > 55 mg²/dL² and despite phosphorus lowering therapy for ≥ 14 days
	
 
CTCAE Grade 2 for > 7 consecutive days
 
CTCAE Grade ≥ 3
 

**Table 7.** Criteria for defining dose-limiting toxicities

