# 12.4 Primary Safety Analysis

Cohort 1 (infigratinib plus tamoxifen) will follow the 3+3 design evaluating 3 infigratinib doses levels, starting at 100 mg infigratinib 3 weeks on/1 week off) and moving to, if needed, 75 mg or 125 mg infigratinib 3 weeks on/1 week off. Given the nature of this cohort to be a safety run-in and the limited number of available subjects for this population, intra-subject dose-escalation will be allowed. The risk with intra-subject dose-escalation is that a dose may be declared overly toxic when the toxicities should be attributed to the number of cycles rather than the dose, but it is believed this is a conservative approach focused on subject safety.

Initially, 3 subjects will be treated at 100 mg for 2 cycles. If there are no DLTs observed in a subject at 100 mg after 2 cycles, the subject will escalate to 125 mg for 2 additional cycles. If 1 DLT is observed at 100 mg, an additional 3 subjects will be treated at 100 mg. If 2 or more DLTs are observed at 100 mg, an additional 3 subjects will be treated at 75 mg. If 1 DLT is observed at 75 mg, an additional 3 subjects will be treated at 75 mg. If no DLTs are observed in the first 3 subjects at 100 mg, but 1 DLT is observed at 125 mg, an additional 3 subjects will be treated at 125 mg, an additional 3 subjects will be treated at 125 mg. If 2 or more DLTs are observed at 125 mg, Cohort 1 will close. If a dose achieves no DLTs in 3 subjects after 2 cycles or 1 DLT in 6 subjects after 2 cycles, that dose will be declared safe for use in the main phase 2 trial.

If a subject withdraws prior to the completion of the first 2 cycles of therapy without having experienced a DLT, an additional subject will be enrolled at that dose level.

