# 12.7 Analysis Population

All subjects who received at least one dose of the study drug (infigratinib) will be analyzed for the safety and efficacy outcomes outlined in sections 12.4; 12.5; and 12.6.

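### DLT evaluability does not require tamoxifen exposure, so the combination can be cleared partly on subjects who have stopped tamoxifen

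*Combined protocol and SAP*

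**What the plan says.** Section 1.1 sets the primary objective as the highest infigratinib dose, up to 125 mg, for use with standard tamoxifen. Section 12.9 accepts the combination for future studies if the Section 12.4 rule is met. That rule is "If a dose achieves no DLTs in 3 subjects after 2 cycles or 1 DLT in 6 subjects after 2 cycles".

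Four provisions decide who counts and what counts:

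- **DLT definition (10.1).** The event must be "at least possibly related to therapy with infigratinib". The criteria in Table 7 are "pre-specified based on the pre-clinical toxicity of infigratinib". Tamoxifen is not named.
- **Stopping tamoxifen (4).** If toxicity is judged related to tamoxifen and not to infigratinib, "subjects will be given the option of continuing infigratinib only (without endocrine therapy) until progression". The DLT window is not excepted.
- **Replacement (12.4).** The rule applies "If a subject withdraws prior to the completion of the first 2 cycles of therapy without having experienced a DLT". Stopping tamoxifen alone is not mentioned.
- **Population (12.7).** "All subjects who received at least one dose of the study drug (infigratinib) will be analyzed for the safety and efficacy outcomes". The outcomes of Section 12.4 are expressly included, and only infigratinib exposure is required.

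Sections 10.1 and 12.4 also move a subject without a DLT at 100 mg to 125 mg for Cycles 3 and 4, with no condition on tamoxifen exposure. Section 7.3 already records "relationship to study drug (infigratinib or tamoxifen") for every adverse event.

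**The concern.** Taken together, these rules allow the following sequence. A subject has an event in Cycle 1 that the investigator puts down to tamoxifen alone. It is not a DLT. The subject stops tamoxifen, continues infigratinib, completes two cycles and is counted as one DLT-free subject for the combination. The subject then moves to 125 mg and supplies data for that level too. Nothing in the plan removes or flags this subject.

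The decision rests on 3 to 12 subjects. One subject off tamoxifen is a third of a 0-of-3 clearance, and by then shows only how infigratinib alone is tolerated. The subjects lost in this way are those who tolerated the combination least well, so any error runs towards clearing the dose. Attribution between the two drugs is also a judgement made in an unmasked study.

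**Working it through.** **The plan's own figure.** The Synopsis gives 3 to 12 evaluable subjects before replacement. Following the paths in 12.4:

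- Minimum: 3 subjects at 100 mg without a DLT, and the same 3 at 125 mg, makes 3.
- Maximum: 6 at 100 mg, then 6 at 75 mg, makes 12.

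Both reproduce.

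**Loss of information when a subject stops tamoxifen.** With 0 DLTs in n subjects, the one-sided 95% upper bound is 1 − 0.05^(1/n):

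- n = 3 on both drugs: 63%
- n = 2: 78%
- n = 1: 95%

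**How often this could happen.** The documents give no rate for stopping tamoxifen. For an assumed chance d per subject within the window, the chance of at least one such subject among n is 1 − (1 − d)^n, and of all three is d³.

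| d (assumed) | At least 1 of 3 | At least 1 of 6 | All 3 of 3 |
|---|---|---|---|
| 5% | 14% | 26% | 0.01% |
| 10% | 27% | 47% | 0.1% |
| 20% | 49% | 74% | 0.8% |

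The usual effect is therefore dilution.

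**Effect of the attribution rule.** For a DLT rate p, the chance that a dose is cleared is (1 − p)³ + 3p(1 − p)² × (1 − p)³. For the infigratinib rate I use the single-agent results in Section 2.2.9: 1 of 6 at 100 mg and 1 of 8 at 125 mg. At p = 1/6 this gives 0.579 + 0.201 = 0.780.

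If events due only to tamoxifen also counted, at rate q and independently, the total rate would be 1 − (1 − p)(1 − q). The documents give no value for q. Section 7.1.2 lists thrombotic events on tamoxifen at 0.8%, 0.5% and 0.4%, which add to 1.7%. I use that as one illustration and add 5% and 10% as plain assumptions. For example, p = 1/6 and q = 10% give 1 − 0.833 × 0.90 = 0.25, and a clearance chance of 0.422 + 0.178 = 0.600.

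| Infigratinib rate | As written | q = 1.7% | q = 5% | q = 10% |
|---|---|---|---|---|
| 1/6 | 0.780 | 0.750 | 0.691 | 0.600 |
| 1/8 | 0.862 | 0.834 | 0.775 | 0.681 |

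The difference is about 3, 9 and 18 percentage points at either infigratinib rate.

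**The case against.** The strongest reply is that the trial varies only infigratinib. Tamoxifen is fixed at its approved dose, so an event that infigratinib did not cause should not move the infigratinib dose. Tamoxifen-related events are still recorded under 7.3, tabulated under 12.5 and, if serious, reviewed under 11.3. This is a fair defence of the attribution rule. It does not answer the evaluability gap: a subject who has stopped tamoxifen says little about the combination, however the event was attributed.

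It can also be said that no sentence expressly keeps these subjects in the count. Section 12.7, read literally as the DLT-evaluable set, would also keep the early withdrawers whom 12.4 replaces, so it may be meant as a reporting population. That stands. Retention follows from 12.7 together with the silence of 12.4. On the other reading, their handling in the primary count is undefined, which also needs correcting.

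A reader might infer four stronger points that the documents do not support:

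- **That the combination would be cleared wholly on subjects off tamoxifen.** This is possible, but at most 0.8% for three subjects across the range above. The word is partly.
- **That toxicity of the combination escapes the DLT definition.** Events possibly due to both drugs, or of uncertain cause, already meet the threshold in 10.1. Only events judged wholly due to tamoxifen fall outside it.
- **That the clearance probability is inflated by some 20 points.** That needs a tamoxifen-only rate of about 10% or more, for which the documents offer nothing. The 1.7% covers thrombotic events only and carries no grade, so it is neither a DLT rate nor a ceiling.
- **That 10.1 and Table 7 contradict each other.** The skipped-dose row of Table 7 says "considered at least possibly, probably, or definitely related to the study drug", but that row is about failure to give infigratinib, and Sections 7.1.1 and 12.7 use the same term for infigratinib. Section 7.3 is a list of CRF fields naming both agents, and 10.3.1 says only that the event is related. This is loose terminology that is worth tidying.

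**Conclusion.** The point holds in a limited form. The primary question concerns two drugs given together, while evaluability for it depends on one. As written, a subject off tamoxifen can count towards the clearance of a dose and towards the 125 mg data.

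If one of three subjects in a clean cohort is off tamoxifen, the upper bound on the combination's DLT rate moves from 63% to 78%. That figure needs no assumption about tamoxifen toxicity. The attribution gap is narrower. Its effect on the chance of clearance is about 3 to 18 points for assumed tamoxifen-only rates of 1.7% to 10%, taken as independent of infigratinib DLTs and with the small single-agent cohorts supplying the infigratinib rate. The direction is always towards clearing the dose; the size is not known. The plan should be corrected, but this does not invalidate the design.

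**What to change.** 1. **Sections 12.4 and 12.7.** State that a subject who stops tamoxifen inside the DLT window for a dose level, without a DLT, is not evaluable for the combination at that level and is replaced. The window should be defined per dose level, because the present replacement wording covers only the first two cycles of therapy and so misses Cycles 3 and 4 at 125 mg. Separate the DLT-evaluable set from the all-treated safety population.
2. **Sections 10.1 (with Table 7), 7.3 and 10.3.1.** Reconcile the wording so that DLT attribution is stated for the combination, meaning at least possibly related to either drug. If the infigratinib-only rule is kept for dose decisions, report the DLT count both ways.

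The two changes belong together. Replacement alone would remove from the count a subject who had a severe event put down to tamoxifen. The option in Section 4 to continue infigratinib alone need not change, since only evaluability is affected.

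The cost is amendment wording, an occasional replacement subject (the Synopsis total already excludes replacements), and an occasional tamoxifen-driven DLT that makes clearance somewhat more conservative. No new data are needed, because 7.3 already collects the relationship to each drug.

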Grade 4 (> 5.0 × ULN)	For any Grade 4 asymptomatic lipase or amylase elevation, infigratinib should be held and continuation of therapy should be discussed with the medical monitor following resolution to ≤ Grade 2.						
Hyperphosphatemia							
Serum phosphorus > 5.5 to 7.0 mg/dL	Maintain dose level of infigratinib and optimize phosphate lowering therapy (see "Management of Hyperphosphatemia" in Section 4.2).						
Serum phosphorus > 7.0 mg/dL	If serum phosphorus is > 7.0 mg/dL, serum phosphorus should be monitored every 2 to 3 days until ≤ 7.0 mg/dL.						
	For serum phosphorus that is > 7.0 mg/dL for more than 7 days, or for a single serum phosphorus > 9.0 mg/dL:						
	
 
Hold infigratinib dose until resolved to serum phosphorus ≤ 5.5 mg/dL.
 
						
	For serum phosphorus that is > 7.0 mg/dL for more than 7 days:						
	
 
Restart infigratinib at the same dose level with increased phosphate binder dosing if the subject did not receive maximal phosphate binder dosing (sevelamer 1600 mg 3 times daily).
 
						
	
 
Reduce one dose level of infigratinib if the subject had received maximal phosphate lowering therapy (sevelamer 1600 mg three times daily). Continue maximal phosphate binder dosing.
 
						
	For serum phosphorus that is > 9.0 mg/dL:						
	
 
Reduce one dose level of infigratinib. Restart infigratinib with maximal phosphate binder dosing.
 
						
	It is recommended that phosphate binder dosing continues during infigratinib dose interruptions for hyperphosphatemia.						

**Table 6.** Criteria for Interruption and Re-initiation of Infigratinib for AEs Considered to be Possibly Related to Infigratinib

Worst Toxicity CTCAE (v5.0) Grade (Unless Otherwise Specified)	Recommended Dose Modifications any Time During a Cycle of Therapy
Hypercalcemia	
Serum calcium Grade 2	
 
Hold infigratinib dose until resolved to Grade 1 or baseline:
 
If resolved within ≤ 7 days after suspending infigratinib, maintain dose level
 
If resolved between > 7 days and 14 days after suspending infigratinib, decrease by 1 dose level
 

	If not resolved within ≤ 14 days, discontinue infigratinib
Serum calcium ≥ Grade 3	Discontinue subject from study drug
	NERVOUS SYSTEM DISORDERS
Any Grade 2 neurotoxicity	Omit dose of infigratinib until resolved to CTCAE Grade ≤ 1, then decrease by 1 dose level of infigratinib  • If not resolved within ≤ 14 days, discontinue infigratinib

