### 10.3.1 Primary Outcome

**Primary Outcome Title**: Dose-limiting Toxicity (DLT)

**Primary Outcome Measure Description**: The primary outcome for this study is dose-limiting toxicities (DLTs) during the first 2 cycles of therapy at a specific dose. All grades per the Common Terminology Criteria for Adverse Events (CTCAE). DLT is defined as a related and clinically-significant adverse event (AE), including missed doses due to a related AE. Due to limited number of characters that can present in this field, it is not possible to consistently provide additional details across all sub-elements of this outcome. See protocol. The outcome is expressed as the number of DLT events by the assigned infigratinib dose level, a number without dispersion.

Time Frame: 8 weeks.

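### The skipped-dose DLT criterion does not say whether its 16 of 21 days are days missed or days given, so a subject with 6 to 15 related missed doses can be a DLT or not

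*Combined protocol and SAP*

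**What the plan says.** Section 10.1 states: "The primary endpoint is the incidence of dose-limiting toxicities (DLTs) in the first 2 cycles of therapy at a specific dose". Table 7 then lists the qualifying events. Its first row reads "The inability to administer infigratinib on ≥ 75% of scheduled treatment days during cycle 1 at that dose (ie, ≥ 16 days", and the bracketed gloss in full is "ie, ≥ 16 days of the 21 days of planned treatment". The cause must be of a stated kind: "due to unresolved adverse event of any grade and considered at least possibly, probably, or definitely related to the study drug". A second part of the row covers a second cycle delayed because a related event has not recovered by Day 43.

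Section 10.3.1, the registry summary, mentions the criterion only as "including missed doses due to a related AE". It gives no threshold and refers the reader to the protocol.

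Section 12.4 feeds the DLT count into the 3+3 rule:
- 0 DLTs in 3 subjects, or 1 in 6, declares a dose safe.
- 1 DLT at 100 mg adds 3 subjects at that dose.
- 2 or more DLTs at 100 mg move the study to 75 mg.
- 2 or more DLTs at 125 mg close the cohort.
- A subject with no DLT after two cycles at 100 mg goes up to 125 mg.

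**The concern.** The row joins a word of failure (inability) to a figure that looks like a completion target (at least 75%). It can mean that dosing failed on at least 16 days. It can also mean that dosing on at least 16 days was not achieved. The gloss repeats the number without giving its direction, and no other section supplies it.

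This is the Table 7 criterion that catches subjects kept off drug by related toxicity of any grade. Under one permitted reading, a subject who missed 15 of 21 doses for a related event counts as DLT-free. Groups of three are small enough for one subject to decide the dose, so two assessors applying the same text could reach different dose decisions from the same data. On the wording of sections 10.1 and 12.4, the classification also decides whether that subject goes up to 125 mg.

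**Working it through.** **The plan's own figure.** Section 4 gives "infigratinib orally daily 3 weeks on, 1 week off (28-day cycle"), so 21 treatment days per cycle. 0.75 × 21 = 15.75, rounded up to 16, and 16/21 = 76.2%. The figure of 16 is correct arithmetic. It fits either reading, so it does not settle the direction.

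**The two readings by doses missed (0 to 21).**

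| Doses missed | Doses given | DLT if 16 or more missed | DLT if fewer than 16 given |
|---|---|---|---|
| 0–5 | 16–21 | no | no |
| 6–15 | 6–15 | no | yes |
| 16–21 | 0–5 | yes | yes |

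They disagree on 10 of the 22 possible counts. That is a span of counts, not a probability.

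**Can a subject be in the zone and meet no other row?** Yes. Two examples built from the protocol's own rules:

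- *Grade 2 neurotoxicity.* Table 6 omits infigratinib until Grade 1 or less. A hold of 10 treatment days gives 10 missed doses. Table 7's general row needs Grade 3 or 4, and recovery before Day 43 avoids the delay criterion.
- *Phosphorus.* Section 4.1.2 checks phosphorus on Days 4 and 15 of Cycle 1. Suppose phosphorus-lowering therapy starts on Day 4 and the Day 15 value is 9.5 mg/dL. For a value above 9.0, Table 6 says "Hold infigratinib dose until resolved to serum phosphorus ≤ 5.5 mg/dL". If infigratinib is held from Day 15 through Day 21, 7 doses are missed and 14/21 = 66.7% are given. The Table 7 phosphorus criteria need at least 14 days of prior therapy (here 15 − 4 = 11) or a value above 10.0. If phosphorus is at or below 9.0 once 14 days of therapy are reached, and at or below 7.0 within a week, none of them is met. The skipped-dose row alone then decides.

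**Effect on one group of three (section 12.4).** One zone subject turns 0/3 into 1/3, or 1/3 into 2/3. Two zone subjects turn 0/3 into 2/3.

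**Effect on the chance that a dose is declared safe.** Let p be the probability of a DLT per subject, with subjects independent and one dose level considered alone:

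P(safe) = (1−p)³ + 3p(1−p)² × (1−p)³

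Under the 16-missed reading, p is the base rate b from all other criteria (including 16 or more missed). Under the completion reading, p = b + q, where q is the share of subjects in the zone who meet no other row. Both b and q are assumed. For orientation only, section 2.2.9 reports single-agent DLTs of 1/6 (16.7%) at 100 mg and 1/8 (12.5%) at 125 mg.

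Example, b = 10%, q = 5%: at p = 0.10, 0.729 + 0.177 = 0.906; at p = 0.15, 0.614 + 0.200 = 0.814. The fall is 9 points.

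| b | q = 0 | q = 5% | q = 10% | q = 20% | Fall, points |
|---|---|---|---|---|---|
| 10% | 0.906 | 0.814 | 0.709 | 0.494 | 9 / 20 / 41 |
| 16.7% | 0.780 | 0.672 | 0.564 | 0.366 | 11 / 22 / 41 |
| 25% | 0.600 | 0.494 | 0.396 | 0.234 | 11 / 20 / 37 |

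The chance of at least one zone subject among three is 1 − (1−q)³: 14%, 27% and 49% for q = 5%, 10% and 20%.

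**The case against.** The strongest reply is that context shows the intent. Many Table 6 rows discontinue infigratinib when an event has not resolved within 14 days, and some within 7. One continuous hold reaches 16 missed days only if it starts by Day 6 (Days 6 to 21 are 16 days), so the 16-missed reading leaves the row almost idle. This is fair evidence for the completion reading. It does not put the direction into the text, and a primary-endpoint criterion should not rest on inferred intent.

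A second reply is that the zone is narrower than 6 to 15 missed doses suggests. That stands. Other Table 7 rows already catch Grade 2 creatinine or calcium elevation, Grade 3 transaminase elevation, Grade 3 fatigue and Grade 3 or higher neutropenia when they last more than 7 days. They also catch amylase or lipase elevation not reversed within 7 days, and most other Grade 3–4 non-hematological events. Section 10.1 also counts events that lead to failure of the re-treatment criteria, which may cover holds ending in discontinuation. What remains is mainly Grade 2 holds and some phosphorus holds.

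Four stronger inferences are tempting, and the documents do not support them:

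- *That 16 or more missed is the literal meaning.* Both readings are grammatical.
- *That section 10.3.1 conflicts with Table 7 by counting missed doses over both cycles.* It gives missed doses no threshold and no cycle scope, says space is limited, and defers to the protocol. Restricting the count to cycle 1 at a dose may be deliberate.
- *That many Table 6 holds last 7 to 14 days.* Table 6 gives cut-offs for resolution, not durations. The median interruption of 7 days in section 2.2.9 came from continuous dosing, with a median onset of 22 days, which is after the 21-day block.
- *That a single figure describes the loss in the chance of declaring a dose safe.* The zone share is unknown, so only a range on stated assumptions can be given.

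**Conclusion.** The point holds as an ambiguity in a primary-endpoint rule. Subjects with 6 to 15 related missed doses in cycle 1 at a dose, and no other Table 7 event, are DLTs under one permitted reading and not under the other. The effect on a single 3+3 decision is certain once such a subject occurs.

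How often that would happen cannot be estimated from the documents. The difference of about 9 to 41 percentage points in the chance of declaring a dose safe rests on assumed base rates of 10% to 25%, assumed zone shares of 5% to 20%, independent subjects and one dose level taken alone. A smaller zone share would give a smaller difference. The finding does not show that either threshold is wrong, nor that the row must extend to the second cycle.

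**What to change.** Before any dose decision, the clinical team should reconcile the row and restate it as one whole-number count out of the 21 planned doses, labelled as doses missed or doses given. In those terms the two current readings are 16 or more missed (5 or fewer given) and 6 or more missed (15 or fewer given). This review does not say which is right. Any subject already assessed with 6 to 15 related missed doses should be checked against the settled wording.

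The cost is one table row in an amendment, with no change to the design or sample size. DLT counts may rise if the completion reading is the one intended and the other has been applied.
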